## **12.0 Local Number of Subjects**

Anticipated enrollment: 270 YMSM

## **13.0 Recruitment Methods**

### **SRV initiated recruitment and outreach**

YMHP will utilize three SRVs (University of Miami, Wayne State University, and Children’s Hospital of Philadelphia) to complete clinic- and field-based recruitment. All three SRVs have extensive relations with the gay, bisexual, and transgender communities, community service organizations, and local health service organizations, and are providers for MSM. In this aspect, recruitment will occur via routine walk-in visits for HIV testing at their clinics, mobile HIV testing at outreach events, and outreach at events for HIV testing at the clinic. Information about the study will be included in the IRB-approved flyers, brochures and cards, customized for each SRV. Study-related recruitment information will be displayed in waiting rooms and exam rooms at each clinic and will be distributed to potential participants at mobile testing events and local

PROTOCOL TITLE: Comparative effectiveness trial of clinic-based delivery of an HIV risk reduction intervention (YMHP) for YMSM, Phase 2

outreach efforts. The recruitment materials both encourage HIV testing and promote the YMHP study.

Community health workers (CHWs) who conduct standard of care HIV testing services for the YMHP SRVs will be trained to provide information about the YMHP study after HIV-negative results are delivered at the clinic or in the field at mobile testing events. The CHW will be trained in appropriate and ethical methods of recruiting participants in clinical settings and in the field. To minimize the risk for coercion, the staff member and the study information will emphasize the optional nature of participation and that it will not affect, in any way, their access to healthcare services. If the potential participant is interested in finding out if he is eligible for YMHP after learning about the study, the CHW will provide an iPad with a secure online Qualtrics YMHP Study Screener (attached to this IRB application). The confidential YMHP study screener will be completed on the iPad by the potential participant and no one will be able to see the responses; the iPad will only indicate whether the potential participant is eligible. CHWs may also collect contact information to send the study screener to participant via text or email so they can complete the screener at a later time. We have found that potential participants may not want to screen at an outreach event or venue.

YMSM who test HIV-negative at a clinic site or through mobile testing efforts provided by community collaborators in the field will be informed about the opportunity to participate in the YMHP study by study staff members who are certified to conduct HIV testing. Individuals who are determined eligible for the study will be contacted by the YMHP Research Assistant at one of the participating SRVs to schedule an appointment to learn more about the study and review the study consent or assent form. Individuals who test negative and are determined to be eligible for the study on location (i.e. at partnering clinic site) will be able to schedule an appointment after contact information is collected.

Only those who screen eligible for YMHP via the confidential study screener will continue to the next survey link on the iPad. Those eligible will complete an electronic Locator Form (attached to this IRB application). The information provided by the potential participant on the Locator Form will be used by the Research Assistants to contact the potential participant to make an appointment at one of the YMHP SRVs. At the appointment, study staff will review the consent or assent form with the potential participant. If the participant provides consent, a baseline appointment will take place. At the conclusion of the baseline appointment, only those who meet inclusion and do not meet exclusion criteria will be considered eligible for randomization in YMHP.

YMSM who screen ineligible for the study do not need to provide contact information and may screen again after 30 or more days, provided they tested HIV-negative at the clinic site in the past 90 days or they again test HIV-negative at the clinic site. Participants are also able to re-screen should they test HIV-negative at the clinic site or through mobile testing efforts associated with the clinic site.

### **Participant Referrals for Recruitment**

Sites will also be asking enrolled participants to refer their friends to screen for YMHP. Participants who complete the baseline appointment will be provided up YMHP study cards with

**PROTOCOL TITLE:** Comparative effectiveness trial of clinic-based delivery of an HIV risk reduction intervention (YMHP) for YMSM, Phase 2

a unique ID on them. Or they will be given an electronic link to the study screener with a unique ID embedded into the URL, which will track study screeners completed and connected to that participant. They can give these cards or send the link to friends who may be interested in screening and participating into the study. For each friend (up to 5) who takes the study screener, is eligible, and shows for a baseline appointment, the participant who referred them will receive \$10 gift card (up to \$50).

**PRIDE-initiated Online Recruitment**

The PRIDE Health Research Consortium (formerly the Center for HIV Educational Studies & Training (CHEST)) at Hunter College will use a variety of recruitment strategies to also recruit participants for this study.

PRIDE will assist in referring potentially eligible participants to the YMHP study through existing online recruitment efforts. PRIDE utilizes the Hunter College IRB-approved Online Master Screener (OMS) to preliminarily screen individuals who are interested in participating in studies being conducted through PRIDE. The OMS, in this instance, will primarily be used as a referral mechanism for the study, directing participants to which study they may be eligible for, including YMHP. If an individual is preliminarily eligible for a study, the individual is asked to provide contact information to PRIDE for follow up. For the purposes of this study, the OMS will only be used to refer potentially eligible YMSM to HIV testing sites by sending them an email referral informing them about the YMHP study. YMSM who complete the OMS and screen preliminarily eligible, will be called for phone screening to determine study eligibility. If they are eligible, they will be referred to the ATN clinic for the Baseline appointment. The contact information collected through the OMS will not be provided to the HIV testing clinic sites. However, YMHP clinic sites will be made aware that a potentially eligible YMSM has been referred to their testing services for the study.

Potential Participants may be identified through online social media and dating apps (e.g., Facebook, Instagram, Reddit, Tumbler, Grindr, Scruff, Adam4Adam). While advertising will be distributed through SIU's REC, they will be targeted to the geographic areas surrounding the ATN sites for this project and will contain information about participation at the ATN clinic.

**Contact information**

Once deemed eligible by the study screener, the individual will be automatically rerouted to a separate Qualtrics locator form to provide his contact information. Participants will be asked to provide a home address and zip code, working phone number, valid email address, and/or handles or URLs to be contacted via social media (e.g., Facebook, Instagram, and Snapchat). The locator form asks participants if messages can be left at the numbers provided. Research staff will not leave messages unless expressly permitted to do so by the participant, as documented on this locator form. If permission is given to leave messages, the research staff will assure participants that messages left with a family member or friend will only ask the participant to contact study staff as indicated on the locator form and will not include any protected health information (PHI) or information related to study participation. The research staff will identify the study as-requested by the participant on the locator form (e.g. "Hunter College"). At the

**PROTOCOL TITLE:** Comparative effectiveness trial of clinic-based delivery of an HIV risk reduction intervention (YMHP) for YMSM, Phase 2

baseline appointment, after fully consenting to participation in the study, each participant will be asked to provide valid contact information for a family member and/or friend who can be called in the event that the participant cannot be reached by phone, email or other contact information provided. Scheduling and reminders about study activities will take place via email, text message, and/or phone.

Information gathered from the electronic locator form will be password protected on the PRIDE Health Research Consortium server. The information will be password protected in a REDCap contact database that will be accessible by REC and authorized SRV study staff. Contact information will be kept separate from all other study records, with access limited to designated research personnel. The contact information should be updated every time there is contact with the participant.

## 14.0 Withdrawal of Subjects

### Criteria for Premature Discontinuation

Below, there are categories of “dropping” participants along with their definitions. These categories should be accurately used in the site’s tracking materials if one of the conditions below occurs.

Category: Definition	Procedure	Notes
Refused BL (Prior to Consent): Screened eligible, but never shows up for appointment and/or no longer wishes to be contacted.	Remove from rescheduling call lists and mark as “Do Not Contact” in REDCap.	Counted towards screened number only.
Withdrew during BL (After Consent): Provided consent but refused to finish BL appointment.	Mark as “Baseline concluded” but not “Baseline completed”	Counted towards screened number only; these participants get marked as “Withdrew from Study” for sIRB purposes.
Withdrew after BL (After Consent): Participant completed the BL but asked to be removed from the study thereafter.	Remove from Follow Up Call Lists; should be Tracked as enrolled. If the withdrawal occurs after randomization, they should remain in the randomizer and count towards randomized totals. If the withdrawal occurs after baseline completion but before randomization, do not randomize.	Counted towards enrolled total. If randomized, the participant also counts towards randomized total and stays in all denominators for Follow Up retention; these participants get marked as “Withdrew from Study” for sIRB purposes.
Ineligible during BL (After Consent): Provided consent but was found to be Ineligible during the BL appointment.	Mark as “Baseline concluded” but not “Baseline completed” They should not be randomized	Counted up to and including in the enrolled number; these participants get marked as “Withdrew from Study” for sIRB purposes.

PROTOCOL TITLE: Comparative effectiveness trial of clinic-based delivery of an HIV risk reduction intervention (YMHP) for YMSM, Phase 2

Ineligible after BL (After Consent): Participant either completed the BL, both BL and sessions, OR all BL, sessions and follow-ups but was found ineligible for enrollment at a later date (e.g., found to have psychiatric conditions while collecting BL data◊)	Remove from Follow Up Call Lists; should be Tracked as enrolled and have a condition assigned	Counted up to and including randomized/enrolled and stays in all denominators for Follow Up retention; these participants get marked as “Withdrew from Study” for sIRB purposes.
Refused intervention (if applicable), Still Enrolled: Participants who are no longer interested in the intervention sessions, but have indicated a willingness to continue to be followed for Follow Up Visits	Remain in Database to be called for Follow Up visits	Treated as other enrolled participants except they wouldn't show up on session-specific call lists.
Passed away: Participant was enrolled but later passed away	Notify REC immediately with details regarding the situation (i.e. Date of Death, Date Notified, Cause of Death, Participant Age and Sex); Remove from Follow Up Call Lists	Counted up to and including randomized/enrolled and stays in all denominators for Follow Up retention; these participants get marked as “Withdrew from Study” for sIRB purposes.
Withdrawn from the study by the Research Team: Participant was enrolled but later dismissed from the study by the Protocol Lead	If a participant is administratively dismissed from the study by the Protocol Lead for being verbally abusive to staff and we do not plan on re-engaging them.	Treated as other enrolled participants except they wouldn't show up on follow-up call lists and should be marked as Do Not Contact (DNC) in the database; these participants get marked as “Withdrew from Study” for sIRB purposes.
Other	If a participant withdraws for any other reason not listed here, please contact the REC immediately to discuss how to proceed.	

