## **6.0 Procedures Involved**

### **Enrollment and Consent**

Utilizing enrollment procedures established within ATN, SRV staff will invite YMSM who are identified through outreach, at their clinic, or through mobile testing efforts to screen for the study. Those interested will complete a brief iPad eligibility screener. HIV testing may be conducted after the screener and before the baseline appointment. If eligible on the screener, SRV study staff will schedule the potential participant for a baseline assessment. Potential participants will complete informed consent following ATN-wide established protocols. This will occur at the beginning of the baseline visit, prior to assessment, but after any HIV testing.

After a potentially eligible participant has given their informed consent to participate in the study, they are then asked to complete the baseline CASI and complete STI testing. Participants are deemed eligible for the study based on screening data and no longer need verification at baseline appointment.

Participants who were enrolled prior to November 1, 2019 will be given a consent/assent addendum at their next follow-up appointment which introduces the long-chain referral and qualitative interview options. Since their initial consent form did not include these items, the addendum will give them the option to receive incentives for providing referrals to the study and to participate in the optional qualitative interview.

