1.2.1 Power Analysis

First, we analyzed power assuming independence of participant observations (assuming that the nesting of people-within-clinic was irrelevant). With regard to STIs, we utilized the “repeated measures” module of PASS 13.0 to examine power to detect odds ratio differences in a repeated measures design. Specifying compound symmetry, we allowed ρ to vary between .2 and .5. Assuming the prevalence of STIs in the remote-based condition varies between .05 and .15, the proposed design ($N = 270$) has power .80 to detect an odds ratio of .20 to .50. Similarly, with regard to the odds of PrEP uptake, allowing the rate of uptake in the remote-based condition to vary between .05 and .20 and allowing ρ to vary between .4 and .7, the proposed design has power of .80 to detect an odds ratio of 1.9 to 2.3. With regard to number of alcohol and drug use days, we utilized the *Tests for Two Poisson Means* module in PASS 13.0. Based data from our previous studies, we allowed the rate of heavy drinking in the phone-based condition to vary between 7 and 9 days during a 30-day assessment. The study is adequately powered to detect a 3% reduction in number of heavy drinking days in the clinic-based condition at any single follow up point. Allowing the rate of drug use in the remote-based condition to vary between 3 and 5 days during a 30 day assessment period, the study is adequately powered to detect a 4% reduction in drug use in the clinic-based condition. A similar analysis was conducted with respect to CAS. Based on our previous research, we allowed the rate of CAS in the phone-based condition to vary between 2 and 4 acts in a 30 day assessment period. The study is powered to detect a difference as small as 5% between the remote and clinic-based YMHP conditions. The nesting of individuals within SRVs has the potential to reduce power because substantial variability in outcome across SRVs can obscure level II treatment effects [70, 71]. The design effect can be used to tailor power analyses calculated under assumptions of independence. In the case of a Level I predictor with a fixed effect which is uncorrelated with other covariates in the model, the design effect is equal to the $1 - \rho$, where ρ is the intra-class correlation or the percentage of variance accounted for by variability between SRVs [71]. In previous intervention trials conducted within the ATN [72], between clinic site variability in HIV related outcomes did not differ significantly from zero. Based on the characteristics of ATN clinics, we anticipate a similar absence of variability across clinics, suggesting that the design effect would result in a negligible reduction in power. Finally, a sample size of 270 is sufficient to detect a moderation effect with an f^2 of .02. Cohen [73] designates this as a small effect, however recent work has characterized an effect of this size as moderate to large as applied to moderation [74].

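### Protocol section 14.0 stops follow-up of randomised participants later found ineligible, which discards outcomes from an as-randomised comparison and may do so unevenly by arm

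*Protocol*

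**What the plan says.** The table under Criteria for Premature Discontinuation (Protocol 14.0) sorts participants who leave the study into categories.

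- *Ineligible after BL* covers people who completed baseline only, baseline and sessions, or everything including follow-up, and were later found ineligible. The instruction is "Remove from Follow Up Call Lists; should be Tracked as enrolled and have a condition assigned". They remain in the randomised or enrolled count and in all retention denominators, and are marked as withdrawn for the single IRB.
- *Ineligible during BL* participants must not be randomised, yet are "Counted up to and including in the enrolled number".
- *Withdrew after BL* participants count as enrolled, with the rule: "If the withdrawal occurs after baseline completion but before randomization, do not randomize".
- *Refused intervention, Still Enrolled* participants stay in the database and are called for follow-up.

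On eligibility, Protocol 6.0 (Enrollment and Consent) says: "Participants are deemed eligible for the study based on screening data and no longer need verification at baseline appointment". Protocol 13.0 (SRV initiated recruitment and outreach) says that at the end of the baseline appointment "only those who meet inclusion and do not meet exclusion criteria will be considered eligible for randomization in YMHP".

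Recruitment targets are worded as enrolment: 270 in Protocol 2.0 and 12.0, and 60 per site in 25.0. SAP 1.2.1 says "the proposed design ($N = 270$) has power .80 to detect an odds ratio of .20 to .50", without saying whether 270 means enrolled, randomised or analysed. The SAP defines no analysis set and gives no rule for participants found ineligible late.

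**The concern.** A comparison of arms as randomised needs outcomes on everyone randomised. Here a staff decision made after randomisation ends data collection for some of them, while they still count as randomised. The protocol gives no reason for treating them differently from people who refuse sessions, or from those who decline audio recording, who also continue to follow-up (Protocol 6.0, YMHP sessions).

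The loss need not be balanced. YMHP participants may attend four recorded sessions on sexual risk and substance use. Controls attend none until sessions are offered at the 9-month follow-up. Those topics overlap the entry criteria (substance-use days, condomless anal sex, injection drug use), so staff have more opportunity to learn of ineligibility in one arm, on variables close to the outcomes. If eligibility is not verified at baseline, more such findings are left to emerge after randomisation.

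A second, smaller matter is that a site can approach its enrolment target with people who were never randomised.

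**Working it through.** **1. How similar participants are treated (Protocol 6.0 and 14.0)**

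| Randomised participant who | Counted as randomised | Called for follow-up |
|---|---|---|
| refuses the intervention | yes | yes |
| declines audio recording | yes | yes |
| is found ineligible later | yes | no |

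Only the last row combines continued counting with an end to follow-up that the participant did not ask for. Someone who had already finished all follow-up loses nothing; the others lose whatever visits remain.

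The row has a second difficulty. It includes people who completed only baseline, yet calls for a condition to be assigned. Protocol 6.0 (Randomization) allows randomisation to be postponed after baseline. Read literally, someone already known to be ineligible could then be assigned a condition.

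**2. What the SAP does about it**

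SAP 1.1 uses full-information maximum likelihood under missing at random. SAP 1.2.2 tests for differential attrition and adjusts for baseline predictors. Removal prompted by something disclosed in a session happens after baseline and need not be explained by baseline or other recorded data. Neither step can be relied on to correct it.

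**3. Possible bias (illustration; no rates in the documents)**

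Suppose there is no true effect and the STI rate is .15 in both arms, the top of the SAP's assumed range. Remove a share y of the YMHP arm whose STI rate is q, and compare those remaining. The observed YMHP rate is (.15 - y*q)/(1 - y), and the reference odds are .15/.85 = .1765.

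- y = .05, q = .30: .135/.95 = .1421, odds ratio .94
- y = .10, q = .30: .120/.90 = .1333, odds ratio .87
- y = .05, q = .05: .1475/.95 = .1553, odds ratio 1.04
- y = .10, q = .05: .145/.90 = .1611, odds ratio 1.09

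The direction depends on who is removed. With 135 per arm (1:1 assumed), 5% is about 7 people and 10% about 14.

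**4. The SAP's power figure**

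SAP 1.2.1 omits alpha, sidedness, allocation and the number of repeated measures M, so its full range cannot be reproduced. One corner can: prevalence .15, odds ratio .50 (second rate .0811), correlation .2, M = 4, two-sided .05, 135 per arm. The effective number per arm is 135*4/(1 + 3*.2) = 337.5, giving power .801. M = 4 is an assumption; the schedule has two STI tests after baseline, and M = 2 gives .629.

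From the .801 benchmark, losing 5% of the YMHP arm alone gives .790, and losing 10% gives .777.

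**5. Enrolled versus randomised**

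Take 80% power at 270 as stated. With two-sided .05, power at n is Phi(2.802*sqrt(n/270) - 1.960), where 2.802 = 1.960 + .842. Assume recruitment stops at 270 enrolled and 3-10% are never randomised.

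- 3%: n = 262; 2.760 - 1.960 = .800; power .788
- 10%: n = 243; 2.658 - 1.960 = .698; power .757

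**The case against.** **Uneven loss is not shown.** The row's only example, a psychiatric condition noticed while collecting baseline data, could arise in either arm. Controls also meet a CHW, who sees that an individual risk assessment is done (Protocol 6.0, Randomization), and both arms complete the same later surveys. Criteria such as age and residence have no evident link to sessions. This stands: the documents support a plausible imbalance and no more.

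**A reader might infer that the N behind the power statement will not be delivered.** The documents do not support that. A shortfall needs recruitment to stop at 270 enrolled with no replacement, and no section says it will. The table is introduced as guidance for tracking materials, keeps a separate randomised total, and counts those who withdraw during baseline as screened only.

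**A reader might also attribute a large power loss to section 14.0 by adding general dropout.** An assumed 20% attrition alone takes 270 to 216 and power to about 71%, which has nothing to do with this table.

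**The two parts pull against each other.** If eligibility is not checked at baseline, few people will be found ineligible during it. If it is checked at the end, fewer will be found later. The worst case for both should not be assumed together.

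**Other sample-size problems are larger.** Protocol 1.0 and 25.0 imply 180 rather than 270; at 180 the section 4 benchmark falls to .629. The SAP's power statement also compares delivery formats ("Assuming the prevalence of STIs in the remote-based condition varies between .05 and .15"), not YMHP with standard of care. These are separate points, and restating N would not settle them.

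None of this explains why follow-up should end for someone already randomised who has not asked to leave.

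**Conclusion.** The concern holds in a limited form. It is certain from the text that randomised participants found ineligible late are taken off follow-up while still counted, and that the SAP has no rule for analysing them. Outcomes not collected cannot be recovered, and the planned missing-data methods may not correct the loss.

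Its size is unknown. The apparent odds ratios of .94-.87, or 1.04-1.09 in the other direction, rest on assumed losses of 5-10% in the YMHP arm only, assumed STI rates among those removed, and a comparison of the remaining participants without adjustment. The direct cost in power is about 1-2 points at those losses.

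The difference between enrolled and randomised is secondary. It costs about 1-4 points of power at an assumed 3-10% never randomised, and only if recruitment stops at 270 enrolled. A correction of wording is warranted; a claim that the trial is biased or underpowered for this reason is not.

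**What to change.** 1. In the *Ineligible after BL* row, keep every randomised participant on the follow-up call list unless they withdraw consent or further contact is judged unsafe. Align the *Withdrew from Study* status with this.
2. State in the SAP that all randomised participants are analysed in their assigned arm, including those later found ineligible. Report their number by arm.
3. State that nobody found ineligible before randomisation is assigned a condition, including where randomisation was postponed after baseline.
4. Reconcile Protocol 6.0 and 13.0 into one eligibility check completed before randomisation.
5. Say whether the 270 in SAP 1.2.1 means randomised. Either word the recruitment targets as numbers randomised, or restate power for the number expected to be randomised and followed.

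The cost is a few extra follow-up visits and payments, an amendment to the single-IRB status wording, and slightly lower stated power if the figure is restated.
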